Cover Page for Study Protocol and Informed Voluntary Consent Form

Principal Investigator Name:	[name]
NCT Number:	Not yet
Official Title of Study:	Effects of Carbohydrate Counting Training Versus Standard
	Nutritional and Medical Therapy on Glycemic Control and
	Sarcopenia in Type 2 Diabetes: A Randomized Controlled
	Trial
Document Date:	March 24, 2022

Study Protocol

The Aim of the Study

The aim of this study to evaluate the effects of advanced carbohydrate counting training on anthropometric/body composition, biochemical, and clinical parameters of patients with type 2 diabetes mellitus who receive intensive insulin therapy. In addition, this study also evaluated the sarcopenia status of the patients and the effect of carbohydrate counting training on sarcopenia.

Study Design and Participants:

This study was planned as a randomized, controlled, 24-week study and was conducted with the voluntary participation of individuals with type 2 diabetes who were treated with intensive insulin. The study sample consisted of patients who received outpatient treatment at the Uskudar Diabetes Polyclinic of the Fatih Sultan Mehmet Training and Research Hospital Additional Service Building of the Ministry of Health of the Republic of Turkey between August 2022 and December 2024.

Inclusion criteria included, a history of type 2 diabetes mellitus or using insulin for more than one year, being over 18 years old, receiving basal and bolus insulin treatment, not having received carbohydrate counting training before, not receiving treatment with sulfanylurea drugs from oral anti-diabetics. Exclusion criteria included being pregnant or breastfeeding or planning a pregnancy during the study period, discontinuing insulin treatment during the study period, having active proliferative retinopathy, severe nephropathy, severe or newly diagnosed cardiac disease within 6 months or stage III–IV heart failure, having dementia or psychosis and cognitive impairment, receiving glucocorticoid treatment, being fed enterally or parenterally and receiving nutrition treatment due to another/concomitant disease, having end-stage renal or hepatic/ renal disease (other than proteinuria); having liver disease/microangiopathy diseases, having clinical cancer, chronic respiratory disease or amputations, or having any disease or condition that would prevent completion of the study.

The study was conducted in accordance with the Declaration of Helsinki with the document number E-10840098-772.02-2030 and permission dated 24.03.2022 from the Istanbul Medipol University Non-Interventional Clinical Research Ethics Committee. Informed Voluntary Consent Form was obtained from all volunteers participating in the study.

Research Protocol

The training protocol, duration and content of each training session were decided by doctors and diabetes dietitians. Individual trainings on carbohydrate counting were organized for patients in the training group in 3 sessions on different dates in parallel with carbohydrate counting training levels. The first level training session (90 minutes), provided basic information on nutrition and health and comprised of topics as, macronutrients in food groups and their effect on plasma glucose, glycemic index, healthy food preferences and meal planning, carbohydrate contents in various food items, concept of carbohydrate change (portions of foods containing 15 grams of carbohydrate) were taught. In the second session (45 minutes), the patients calculated the carbohydrate contents of the meals they consumed based on the knowledge from the previous session. In addition, the meal plans, snacking and main meal frequencies, physical activities, effect of insulin doses on plasma glucose, noted down by each patient in their data sheets of each patient were reviewed. In the third training (45 minutes), calculation of the total carbohydrate content of the consumed meal were repeated, in order to reinforce the patient's training in this field. Furthermore, the patients were informed about the Insulin Correction Factor and Carbohydrate/Insulin ratios, and the insulin doses to be taken per meal were calculated and exemplified based on their meal plan data sheets.

Evaluation

A questionnaire form containing sociodemographic information was completed by face-to-face interview method. In addition, biochemical (HbA1c, fasting plasma glucose (FPG), C peptide, total cholesterol, HDL, LDL, triglyceride, estimated glomerular filtration rate) and anthropometric and body composition (weight-height, BMI, fat mass, fat ratio, muscle mass, lean tissue mass, waist circumference), hand grip strength, blood pressure and physical activity measurements of the patients were taken at the beginning, 12th week and 24th week of the study.

Biochemical analyzes of the participants were performed in the Biochemistry Laboratory of Fatih Sultan Mehmet Training and Research Hospital. The individuals participating in the study were asked to give blood in the morning after 10-12 hours of fasting after dinner. Plasma glucose levels were analyzed by hexokinase method in colorimetricspectrophotometric Aeroset (Roche Hitachi cobas 6000) autoanalyzer and total cholesterol, HDL and triglyceride levels were analyzed by enzymatic colorimetric method. LDL levels were calculated using the Fridewald equation [1]. In addition, HbA1c levels were measured by high-performance liquid chromatography (HPLC) method. Serum C peptide levels were determined by Enzyme-Linked Immunosorbent Assay (ELISA) method (Roche Hitachi cobas 6000) using a commercial kit in an autoanalyzer.

Anthropometric measurements of the participants were taken by a dietician. The height of the participants was measured with a wall-type stadiometer with barefoot heels touching each other, arms hanging to the side, feet 45° apart and head in the Frankfort plan. Body weight and body composition were measured with TANITA BC-418MA bioelectrical impedance analyzer. BMI values of the participants were calculated based on weight and height measurement data. In waist circumference measurement, the midpoint between the

bottom of the rib bone and the iliac crest was determined and the circumference of this area was measured with a tape measure.

The participants' hand grip strength was measured three times with a digital hand dynamometer (CAMRY-EH101, USA) and the mean value in kg was calculated. In addition, the threshold values determined for hand grip strength in the European Working Group on Sarcopenia in Older People guideline are 15 kg for women and 20 kg for men [2]. In this context, individuals below this threshold value were evaluated as low muscle strength. Skeletal muscle mass data obtained from the BIA measurement results and skeletal muscle according to the height obtained from this data were calculated by dividing the skeletal muscle mass by the square of the height. In this context, in the European Working Group on Sarcopenia in Older People guideline, the threshold values for evaluation within the scope of sarcopenia were determined as 15 kg for women and 20 kg for men for skeletal muscle, while 5.5 kg/m2 for women and 7 kg/m2 for men for skeletal muscle by height [2]. In this context, individuals below this threshold value were evaluated as having low muscle mass.

In the timed walk-up test, the patient is asked to get up from the chair, walk at a normal walking speed on a flat surface of 3 meters, turn around, walk back and sit back in the chair [3]. The time between the patient getting up from the chair, walking and sitting down again is recorded and the patient's dynamic balance during walking is also evaluated. In addition, the threshold value of the test duration in the evaluation of sarcopenia was determined as 10.85 s in the study by Christopher et al. and individuals above this threshold value were evaluated as low physical performance [4].

Blood pressure of the participants was measured with an automatic sphygmomanometer (SCIAN LD-533, Germany). Three repeated measurements were made on the right arm in the sitting position with the arm at the level of the heart and after a rest period of at least 10 minutes and the mean was calculated. In addition, a 24-hour retrospective food consumption record was applied to evaluate the energy and nutrient intakes. The calculation of the energy, macro and micro-nutrient intakes of the participants was carried out using the Turkish Nutrition Database Ebispro for Windows program (version 7.2) [5].

Reference

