#### **Statical Analysis Plan**

#### Sample Size, Randomization and Formation of Groups

A power analysis was conducted to determine the number of participants to be included in the study. In order to exceed the 80% power level, it was determined that the study should be conducted with 50 individuals (25 participants in the training and 25 participants in the control group), at a significance level was set at 5% with an effect size of 0.518 (df=41; t=1.683) [1].

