### **Statistical Analyses**

The statistical analysis of the data obtained from the study was evaluated using the IBM SPSS Statistics (version 22.0) package program. In order to evaluate the suitability of the data for normal distribution, One-Sample Kolmogorov-Smirnov test was conducted and kurtosis and skewness of the data was evaluated. Independent sample t-test was used to compare two independent groups among with normal distribution, dependent sample t-test and mixed design ANOVA were used to compare repeated measurements between two independent groups. All data have been provided with mean  $\pm$  standard deviation (mean $\pm$ SD). Mann-Whitney U test was used to compare data not showing normal distribution, and Wilcoxon test and Friedman test were used for repeated measurements between two groups. Categorical variables were compared using chi-square test and Fisher's exact chi-square test, and these data were shown with frequency (n, %) values. The significance level between the data was accepted as p=0.05. The graphical representations of the data were evaluated using the GraphPad Prism (version 9.3.0) package program.

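### One exclusion criterion is worded as an event after randomisation, and no available text says that randomised patients are analysed in their assigned arm

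*Protocol*

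**What the plan says.** In the Protocol, Study Design and Participants, the exclusion list contains "discontinuing insulin treatment during the study period" as an item of its own. The inclusion list in the same section requires current basal and bolus insulin. Two other exclusion items also look ahead, but are worded so that they can be judged at entry: "planning a pregnancy during the study period" and "having any disease or condition that would prevent completion of the study".

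Outcomes are measured "at the beginning, 12th week and 24th week of the study" (Protocol, Evaluation). The SAP plans "25 participants in the training and 25 participants in the control group" (Sample Size, Randomization and Formation of Groups). For normally distributed data it says that a dependent-sample t-test and "mixed design ANOVA were used to compare repeated measurements between two independent groups" (Statistical Analyses). That section names software, tests and a significance level, but not which patients enter the tests.

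One part of the SAP, placed before the sample size section, is absent from the copy reviewed, and its content is unknown. Statements here about what the SAP lacks apply only to the parts available.

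**The concern.** A randomised comparison is protected from selection only while the patients analysed are those randomised. A criterion met after randomisation, if it is used to exclude, breaks that protection. In this trial the event is close to the intervention: the third training session deals with correction factors, carbohydrate-to-insulin ratios and the dose for each meal (Protocol, Research Protocol). Stopping insulin could therefore differ between arms and be related to glycaemic outcome.

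The direction of any bias cannot be known in advance. Removing training-arm patients who stopped because control was good would hide benefit. Removing training-arm patients who abandoned the regimen would exaggerate it. For removals from the control arm both directions reverse. If removal is unrelated to outcome, there is no bias.

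The concern is only about who is analysed. It is not about whether or when insulin should be stopped.

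**Working it through.** **1. The wording.** Entry requires current insulin, so an actual stop can only follow entry. The pregnancy item is tied to planning, and the last exclusion item is conditional. The insulin item has neither marker and reads as an event. A planned stop could still be asked about at entry, so the text leaves two readings, and they give two different analysed populations.

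**2. Is there a safeguard elsewhere?** The protocol and the available SAP sections contain no analysis set, no as-assigned rule, no handling of missing data, and no instruction for a patient who meets the criterion after randomisation. They contain no instruction to remove such a patient either, apart from the criterion itself.

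**3. What size could it have?** The plan has no figure of its own to reproduce here, because it gives no discontinuation rate. The illustration below uses one documented input, 25 per arm. Everything else is assumed:

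- k = 1, 2 or 3 patients removed, all from one arm;
- removed patients lie on average D = 0.25, 0.5 or 1 SD from their full-arm mean;
- no true effect, within-arm SD unchanged by removal, one two-sided t-test at 5%.

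Formulas:

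- shift of the arm mean (in SD) = k × D / (25 − k);
- standard error = √(1/(25 − k) + 1/25);
- noncentrality = shift / standard error, with 48 − k degrees of freedom;
- type I error = probability that this noncentral t exceeds the two-sided 5% limits.

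Example, k = 3 and D = 1: shift = 3/22 = 0.136; standard error = √(1/22 + 1/25) = 0.292; noncentrality = 0.136/0.292 = 0.467; type I error 7.4%.

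| D | k | Shift (SD) | Noncentrality | Type I error |
|---|---|---|---|---|
| 0.25 | 1 | 0.010 | 0.036 | 5.0% |
| 0.25 | 2 | 0.022 | 0.075 | 5.1% |
| 0.25 | 3 | 0.034 | 0.117 | 5.1% |
| 0.5 | 1 | 0.021 | 0.073 | 5.1% |
| 0.5 | 2 | 0.043 | 0.150 | 5.2% |
| 0.5 | 3 | 0.068 | 0.233 | 5.6% |
| 1 | 1 | 0.042 | 0.146 | 5.2% |
| 1 | 2 | 0.087 | 0.301 | 6.0% |
| 1 | 3 | 0.136 | 0.467 | 7.4% |

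At D = 0 the error is 5.0% for every k. With equal removals of the same kind from both arms the shift is 0. More removals give larger shifts: 5 of 25 at D = 1 gives 5/20 = 0.25 SD.

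**4. Against the planning effect.** The SAP plans "with an effect size of 0.518" without saying what it measures. If it is read as a standardised difference between arms, the shifts for k = 2 or 3 run from 0.0217/0.518 = 4% to 0.1364/0.518 = 26% of it.

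**The case against.** The strongest reply is that the phrase stands in a list for selecting participants, directly after an item about planning a pregnancy. The idea of planning may have been meant to carry over, or the phrase may be a loose rendering of an intended stop. Harm then needs three things together: the post-randomisation reading, actual discontinuations, and removal related to arm and outcome. The documents establish none of the three. This stands, and it limits the conclusion. It does not settle which reading is in force.

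The absent part of the SAP may hold relevant text. That also stands, so nothing here claims that the complete SAP lacks an analysis set.

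The illustration is assumption throughout and leans towards the larger effect. It places all removals in one arm, holds the SD fixed, and uses a single t-test although the plan also names a repeated-measures analysis. If both arms contain the same k would-be discontinuers, total variance is held at 1 and removal is from one arm only, simulation gives about 5.1% and 5.4% (D = 0.5, k = 2 and 3) and 5.5% and 6.6% (D = 1). The table is therefore not an estimate for this trial.

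A reader might infer that patients were in fact dropped, or that the result favours training because of it. No text reports a removal, and both directions of bias are possible. A reader might also infer that the item could never be screened at entry. That goes too far, since an intention to stop can be asked about.

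**Conclusion.** The point holds in a limited form. The criterion, as worded, is an event after randomisation, and no available text keeps such patients in the arm comparison. Following it literally would break the randomised comparison, so this is more than a missing detail.

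The likely size is small on the assumed values: seven of the nine cases give a type I error of 5.6% or less. The exceptions are 6.0% and 7.4%, when 2 or 3 patients lying 1 SD from their arm mean are removed from one arm only. These figures rest on invented k and D, an unchanged SD and one-sided removal. The documents support no rate, direction or size of actual bias, and an inference that the trial's result is biased would be unsupported.

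**What to change.** The sponsor should reconcile whether the item is an entry criterion or an event after randomisation. This review proposes no rule on insulin.

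Add a short SAP paragraph:

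- The main arm comparison includes all randomised patients in their assigned arm, regardless of insulin discontinuation.
- Every available week-12 or week-24 outcome is used. A patient with only one of these visits is kept, for example through a mixed model for repeated measures. Requiring both visits would come close to a completer set and could still leave removed patients out.
- Where follow-up is ongoing, outcomes are still collected after discontinuation.
- Discontinuations and removals are reported by arm. Any analysis without those patients is a sensitivity analysis only.

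The protocol's past tense and its window "between August 2022 and December 2024" suggest that follow-up may be complete. If so, clarifying the phrase no longer changes the data. The as-assigned analysis should then use all available data, removals should be reported by arm, and the report should acknowledge that uncollected outcomes cannot be recovered.

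The cost is one clarified phrase and one paragraph, with the planned 50 patients unchanged. A small downside is that the estimate includes patients no longer using the skill taught.

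### The low-muscle-mass cut-offs (15/20 kg and 5.5/7 kg/m²) are applied to a BIA muscle quantity whose body region is not named; on the plain reading, total muscle, few patients would be flagged

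*Protocol*

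**What the plan says.** The Protocol's Evaluation section lists the body-composition variables taken at baseline, week 12 and week 24. They include "fat mass, fat ratio, muscle mass, lean tissue mass, waist circumference"; no limb measure is listed. The device is named: "Body weight and body composition were measured with TANITA BC-418MA bioelectrical impedance analyzer". The output used is not.

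For sarcopenia, the same section starts from "Skeletal muscle mass data obtained from the BIA measurement results" and forms the height-adjusted index: "skeletal muscle according to the height obtained from this data were calculated by dividing the skeletal muscle mass by the square of the height". Two pairs of cut-offs follow, both attributed to the European sarcopenia guideline: "15 kg for women and 20 kg for men for skeletal muscle" and "5.5 kg/m2 for women and 7 kg/m2 for men for skeletal muscle by height". The rule is that "individuals below this threshold value were evaluated as having low muscle mass". Which of the two pairs decides is not stated. The pair 15/20 kg also appears, for a different quantity, as the hand-grip cut-offs.

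The SAP text available defines no sarcopenia variable, so this section of the Protocol is the only derivation of the low-mass category.

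**The concern.** A cut-off is meaningful only on the scale for which it was set. Total skeletal muscle, arm-plus-leg muscle and total lean soft tissue differ widely in kilograms, and the Protocol does not say which one is compared with 15/20 kg and 5.5/7 kg/m². With no region named, someone following the text would use the total.

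Sarcopenia is in the trial's title and its stated aim. If the cut-offs lie well below the values most patients have, the low-mass category is almost empty at every visit. With 25 patients per arm it could then show neither change nor a difference between arms, and a low frequency could be reported as a fact about insulin-treated type 2 diabetes when it came from the choice of numerator.

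**Working it through.** The documents give no expected frequency of low muscle mass, no mean or SD of muscle mass, and no BMI limit. There is therefore no figure of the plan's own to reproduce. The cut-offs come from the Protocol (Evaluation); every body-size and body-composition value below is an assumption.

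**1. Are the two pairs on one scale?** Implied height = √(kg cut-off ÷ kg/m² cut-off). Women: √(15/5.5) = 1.65 m. Men: √(20/7) = 1.69 m. Both are ordinary heights, so the pairs agree with each other, and choosing between them does not settle which muscle is meant.

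**2. What falling below the index requires.** A 1.58 m woman needs less than 5.5 × 1.58² = 13.7 kg of muscle, which is 18% of 75 kg. A 1.72 m man needs less than 7 × 1.72² = 20.7 kg, which is 24% of 85 kg. In general, index = BMI × (muscle ÷ body weight), so muscle must be below these shares of body weight:

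| BMI | Women (5.5 ÷ BMI) | Men (7 ÷ BMI) |
|---|---|---|
| 25 | 22.0% | 28.0% |
| 30 | 18.3% | 23.3% |
| 35 | 15.7% | 20.0% |

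**3. Index for assumed patients.** Index = weight × (1 − fat share) × muscle fraction of fat-free mass ÷ height². Two fractions are used: 0.45–0.55 for skeletal muscle and 0.94 for total lean tissue.

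| Assumed patient | Fat-free mass | Index, 0.45–0.55 | Index, 0.94 | Cut-off |
|---|---|---|---|---|
| Woman, 75 kg, 1.58 m, 40% fat | 45.0 kg | 8.1–9.9 | 16.9 | 5.5 |
| Man, 85 kg, 1.72 m, 28% fat | 61.2 kg | 9.3–11.4 | 19.4 | 7 |
| Woman, 50 kg, 1.58 m, 30% fat | 35.0 kg | 6.3–7.7 | – | 5.5 |
| Man, 60 kg, 1.72 m, 20% fat | 48.0 kg | 7.3–8.9 | – | 7 |

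With lean tissue at 95% of fat-free mass, BMI 22–35 and 35–50% fat, the index runs from about 10 to 22 kg/m², so nobody is flagged.

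**4. From single cases to a rate.** A normal tail, Φ((cut-off − mean) ÷ SD), gives:
- Women, SD 1.0: mean 8.0 gives Φ(−2.5) = 0.6%; mean 7.0 gives Φ(−1.5) = 6.7%.
- Men, SD 1.2: mean 10.0 gives Φ(−2.5) = 0.6%; mean 9.0 gives Φ(−1.67) = 4.8%.

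A simulation varied mean BMI over 28, 31 and 34 (SD 5). Mean muscle share of body weight was 24–30% in women and 30–37% in men (SD 3.5 points, falling as BMI rises). Mean height was 1.57 m and 1.71 m. For the limb columns, limbs held about 75% of skeletal muscle.

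| Share flagged | Total muscle, kg/m²: full range | Total muscle, kg/m²: mean BMI 31 | Limb muscle, kg/m²: mean BMI 31 | Total muscle, 15/20 kg: full range |
|---|---|---|---|---|
| Women | 0.02–17% | 0.2–6% | 10–51% | 0.3–35% |
| Men | 0.01–17% | 0.2–5% | 11–55% | 0.04–16% |

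The 17% figures occur only at the lowest BMI combined with the lowest muscle share.

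**5. Per arm of 25.** On total muscle, 17% is at most about 4 patients (25 × 0.17 = 4.25). At mean BMI 31 it is 0 to about 2 (25 × 0.06 = 1.5). On limb muscle at mean BMI 31 it is about 2 to 14 (25 × 0.096 = 2.4; 25 × 0.55 = 13.8).

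**6. The kg rule differs for short women.** Below 1.65 m, 15 kg is the easier of the two cut-offs to fall under. A 1.50 m, 55 kg woman with 40% fat and muscle at 45% of fat-free mass has 33 × 0.45 = 14.85 kg, below 15. Her index is 14.85 ÷ 2.25 = 6.6, above 5.5. Her classification depends on which pair decides.

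**The case against.** The strongest reply is that the Protocol never says whole-body. Silence on region also fits limb values that were used without being described. That stands: what can be shown is an undefined numerator, not a wrong one. Even so, the text would still need the sentence that says which quantity was used.

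Three stronger inferences are tempting, and the documents support none of them:

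- A reader might infer that almost no patient can fall below the cut-offs. The documents give no BMI or muscle-mass distribution, and plausible inputs reach 17% on kg/m². Only the total-lean-tissue case empties the category, and nothing establishes that this output was used. It remains possible, because the variable list has muscle mass and lean tissue mass but no separate skeletal muscle entry.
- A reader might infer that the kg and kg/m² cut-offs fail alike. The 1.50 m woman shows that they do not, and the 15 kg rule reaches 35% of women in the simulation.
- A reader might infer that the guideline sets these values for limb muscle. The guideline is not among the documents, so this has to be checked at source.

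It is also fair to say that one rule applies to both arms, so the choice does not by itself favour either. Muscle mass is recorded as a measurement at three visits, and grip strength and the walk test have their own thresholds. The problem is therefore confined to the low-mass category and to any sarcopenia classification built on it.

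**Conclusion.** The point holds as a defect of definition with a likely practical effect. Read plainly, the rule puts the cut-offs on total muscle. If skeletal muscle is 45–55% of fat-free mass, the assumed 75 kg woman and 85 kg man lie well above them, and few patients would be flagged on kg/m². On the same assumed populations at mean BMI 31, a limb numerator would flag roughly 10–55%. The unnamed numerator therefore largely decides who is called low in muscle mass. The true rate in this clinic cannot be known from the documents, and the direction depends on the plain reading being what was done. Because sarcopenia is in the title and aim, this should be settled before the category is analysed.

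**What to change.** In the Protocol's Evaluation section:

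1. Name the analyser output and the body region used as numerator.
2. Check in the cited guideline which muscle quantity 5.5/7 kg/m² and 15/20 kg refer to, and apply them only to that quantity. If it is limb muscle, use the sum of the arm and leg values divided by height squared, provided the analyser gave those values and they were saved. At the same time, confirm the 15/20 pair, since the same numbers are also given for grip strength.
3. State whether kg, kg/m² or either decides.
4. If no matching quantity is available, do not dichotomise total muscle at these cut-offs; report the index as a continuous outcome.

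The cost is a few lines of text and one re-derived variable. If limb values are needed and were not stored, the low-mass category is lost, along with any sarcopenia classification that requires it.
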